16.3 Stratification Factors

For those treated with nivolumab during chemoradiation (Cohort 1) stratification will be guided by radiation field. Cohort 1A will consist of patients receiving whole pelvic RT, while Cohort 1B will consist of patients receiving extended field RT. No further stratification is anticipated for Cohorts 2 and 3. However, enrollment in Cohort 3 may be revised pending outcomes in Cohort

BrUOG 355: 7/8/17, 7/11/17, 7/20/17, 8/7/17, 8/8/17, 8/14/17, 8/16/17, 8/21/17, 8/22/17, 8/24/17, 8/28/17, 9/5/17, 9/6/17, 9/8/17, 9/11/17, 11/7/17, 11/8/17, 11/19/17 approved DD, 11/20/17, 12/12/17, 12/14/17, 1/29/18, 2/1/18, 2/6/18, 2/7/18, 2/8/18, 2/9/18, 2/12/18, 2/13/18, 3/8/18 all reviews, 3/9/18, 3/13/18, 3/14/18, 3/15/18, 4/19/18, 4/23/18, 5/29/18, 6/5/18, Amendment # 1 7/9/18, Amendment # 2 12/12/18, Amendment #3, 4/6/2020, Amendment #4 5/11/2020

1.

16.4 Analysis of Primary Endpoints

Time-to-event endpoint of progression free survival at 3 years will be described using the method of Kaplan-Meier, and presented with 90% confidence intervals. Patients that are alive without disease progression at time of analysis are censored at the date of last disease evaluation. Acute Treatment-related toxicities that occur during and within six months of study treatment will be summarized by maximum grade and by term using CTCAE v4.0 and reported with 90% binomial exact confidence intervals. Acute toxicities will be used to determine the feasibility within each cohort.

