8.2 Adverse Event Characteristics

This study will utilize the descriptions and grading scales found in the NCI Common Terminology Criteria for Adverse Events (CTCAE) version 4.03 for grading all adverse events. All appropriate treatment areas should have access to a copy of the CTCAE version 4.03. A copy of the CTCAE version 4.03 can be downloaded from the CTEP web site (<http://ctep.cancer.gov>).

BrUOG 355: 7/8/17, 7/11/17, 7/20/17, 8/7/17, 8/8/17, 8/14/17, 8/16/17, 8/21/17, 8/22/17, 8/24/17, 8/28/17, 9/5/17, 9/6/17, 9/8/17, 9/11/17, 11/7/17, 11/8/17, 11/19/17 approved DD, 11/20/17, 12/12/17, 12/14/17, 1/29/18, 2/1/18, 2/6/18, 2/7/18, 2/8/18, 2/9/18, 2/12/18, 2/13/18, 3/8/18 all reviews, 3/9/18, 3/13/18, 3/14/18, 3/15/18, 4/19/18, 4/23/18, 5/29/18, 6/5/18, Amendment # 1 7/9/18, Amendment # 2 12/12/18, Amendment #3, 4/6/2020, Amendment #4 5/11/2020

An Adverse Event (AE) is defined as any untoward medical occurrence in a patient or clinical investigation subject administered a pharmaceutical product and that does not necessarily have to have a causal relationship with this treatment. An AE can therefore be any unfavorable and unintended sign (including an abnormal laboratory finding), symptom, or disease temporally associated with the use of Nivolumab, cisplatin or radiation, whether or not considered related to Nivolumab, cisplatin or radiation. This includes any newly occurring event or previous condition that has increased in severity or frequency since the administration of drug.

During clinical trials, adverse events can be spontaneously reported or elicited during open-ended questioning, examination, or evaluation of a subject. (In order to prevent reporting bias, subjects should not be questioned regarding the specific occurrence of one or more adverse events.)

Adverse events (AEs) will be recorded in the case report form for the duration of the trial, regardless of whether or not the event(s) are considered related to trial medication.

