16 STATISTICAL CONSIDERATIONS

16.1 Study Design/Endpoints

The primary endpoint of this pilot study is to assess the acute toxicity of combining nivolumab with definitive chemoradiation. For the purposes of the study, acute toxicities will be those having onset during or within 30 days of completing treatment. For those receiving nivolumab as maintenance treatment, it will also include those events occurring during or within 30 days of

BrUOG 355: 7/8/17, 7/11/17, 7/20/17, 8/7/17, 8/8/17, 8/14/17, 8/16/17, 8/21/17, 8/22/17, 8/24/17, 8/28/17, 9/5/17, 9/6/17, 9/8/17, 9/11/17, 11/7/17, 11/8/17, 11/19/17 approved DD, 11/20/17, 12/12/17, 12/14/17, 1/29/18, 2/1/18, 2/6/18, 2/7/18, 2/8/18, 2/9/18, 2/12/18, 2/13/18, 3/8/18 all reviews, 3/9/18, 3/13/18, 3/14/18, 3/15/18, 4/19/18, 4/23/18, 5/29/18, 6/5/18, Amendment # 1 7/9/18, Amendment # 2 12/12/18, Amendment #3, 4/6/2020, Amendment #4 5/11/2020

treatment completion.

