16.1.1. Safety review

A safety review for each cohort will be conducted. For cohort 1, safety analysis will occur at the end of chemoradiation. For patients in cohort 2 (who receive nivolumab following chemoradiation), evaluation for safety will occur 4 weeks following initiation of maintenance nivolumab. For patients in cohort 3, safety analyses will occur at the end of chemoradiation and after maintenance therapy has completed.

Criteria that will determine safety will include:

- Grade 3 or higher adverse events that persists for 14 days or longer despite dose-holds and/or maximal medical support. This excludes uncomplicated neutropenia and any laboratory abnormalities deemed by the treating clinician as having no clinical significance
- Inability to complete chemoradiation within 8 weeks

The BrUOG overall PI, the Women & Infants' Hospital site PI (once study is activated), and the Medical Director of BrUOG will review safety data as described to make determinations of feasibility. Enrollment to cohort 2 will not be dependent on the safety review for cohort 1. However, the safety review will be completed for cohort 2, before enrollment begins in cohort 3.

If more than 25% of patients (more than 2 patients in cohort 1 or more than 1 patient in cohort 2) experience a grade 3 or higher adverse event that persists for 14 days or longer, despite dose-holds and/or maximal support, the treatment will be considered not feasible and the next cohort will not be opened.

If more than 25% of patients (more than 2 patients in cohort 1 or more than 1 patient in cohort 2) are unable to complete chemoradiation within 8 weeks, the treatment will be considered not feasible and the next cohort will not be opened.

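### Section 16.4 plans only a treatment-related acute-toxicity table for the primary endpoint, while the feasibility rule in 16.1.1 counts grade 3+ adverse events whatever their cause

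*Combined protocol and SAP*

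**What the plan says.** All references are to the combined protocol and SAP.

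- **16.4, the planned analysis:** "Acute Treatment-related toxicities that occur during and within six months of study treatment will be summarized by maximum grade", by CTCAE term, with 90% exact binomial intervals. It then adds: "Acute toxicities will be used to determine the feasibility within each cohort".
- **16.1, the endpoint:** for this study, "acute toxicities will be those having onset during or within 30 days of completing treatment". Attribution is not mentioned.
- **16.1.1, the feasibility rule:** the first criterion is "Grade 3 or higher adverse events that persists for 14 days or longer despite dose-holds and/or maximal medical support", with the carve-out "This excludes uncomplicated neutropenia and any laboratory abnormalities deemed by the treating clinician as having no clinical significance". The second is "Inability to complete chemoradiation within 8 weeks". The limit for each begins "If more than 25% of patients (more than 2 patients in cohort 1 or more than 1 patient in cohort 2".
- **8.2, the meaning of adverse event:** an event that "does not necessarily have to have a causal relationship with this treatment". The same section has all such events entered in the case report form whether or not they are thought related.
- **8.3.1, attribution:** five levels from definite to unrelated. Section 16.4 does not say which of them count as treatment-related.
- **16.2, the toxicity window:** 30 days after last treatment, against six months in 16.4.

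**The concern.** The primary endpoint of this pilot is acute toxicity, and the one analysis planned for it passes events through an attribution filter. Patients receive nivolumab, cisplatin and radiation, with no control group and no blinding, so whether an event is related is the investigator's opinion. Within a given window the filter can remove patients from the count but cannot add any.

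The feasibility rule has no such filter. A cohort could be closed under 16.1.1 because of events that the primary toxicity table does not contain, and a reader of the results could not reconcile the two. The cut-point on the attribution scale is also unspecified, so it could be set after the data are seen.

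**Working it through.** **1. The plan's own figures.** More than 25% of a cohort means more than 0.25 × n patients: 0.25 × 8 = 2 and 0.25 × 4 = 1. This reproduces the stated limits, so cohort 1 is not feasible at 3 or more of 8 and cohort 2 at 2 or more of 4.

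**2. Scope of events, side by side.**

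| Section | Attribution condition | Window |
|---|---|---|
| 16.1 definition | none stated | onset during, or up to 30 days after, treatment |
| 16.1.1 criterion 1 | none; an adverse event is cause-neutral under 8.2 | at the cohort safety review |
| 16.2 evaluation | none stated | 30 days after last treatment |
| 16.4 table | treatment-related only | six months |

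The only exclusions in 16.1.1 are uncomplicated neutropenia and laboratory findings without clinical significance. Unrelated events are not excluded. No section reconciles the two scopes.

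**3. What one attribution call does.** The exact 90% interval for x of n runs from the 0.05 quantile of Beta(x, n − x + 1) to the 0.95 quantile of Beta(x + 1, n − x). The counts are illustrative and sit at the plan's own limits.

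| Cohort | Any cause | 90% CI | One patient's event called unrelated | 90% CI |
|---|---|---|---|---|
| 1 | 3/8 = 37.5% (not feasible) | 11.1 to 71.1 | 2/8 = 25.0% | 4.6 to 60.0 |
| 2 | 2/4 = 50.0% (not feasible) | 9.8 to 90.2 | 1/4 = 25.0% | 1.3 to 75.1 |

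**4. How often the two counts would fall on opposite sides of the limit.** The documents give neither an expected rate nor a related share, so both are assumptions. Let p be the chance that a patient meets the first 16.1.1 criterion from any cause, and f the share of those patients whose event is called related. Patients are taken as independent. The related count is a subset of the any-cause count, so the probability that the any-cause count crosses the limit and the related count does not is P(Bin(n, p) ≥ r) − P(Bin(n, pf) ≥ r), with r = 3 for n = 8 and r = 2 for n = 4.

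At p = 0.30:

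| Cohort | Any-cause count crosses | Related count crosses, f = 0.90 / 0.75 / 0.50 | Difference |
|---|---|---|---|
| 1 (n = 8) | 0.448 | 0.372 / 0.260 / 0.105 | 0.076 / 0.188 / 0.343 |
| 2 (n = 4) | 0.348 | 0.296 / 0.220 / 0.110 | 0.052 / 0.128 / 0.239 |

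Over p from 0.10 to 0.50 and f from 0.90 to 0.50, the difference ranges from 0.009 to 0.534 in cohort 1 and from 0.009 to 0.426 in cohort 2. It describes how far a related-only display can part from the events behind the decision. It is not the error rate of the decision, which 16.1.1 takes on all causes.

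**The case against.** A reader might infer four stronger things. The documents do not support them.

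- **That feasibility is decided on related events only.** The sentence in 16.4 is "Acute toxicities will be used to determine the feasibility within each cohort", without the word related. Read with the definition in 16.1, it need not carry the filter. The operative rule is 16.1.1, with its own criteria, limits and named review roles. That rule is unaffected.
- **That 16.1 prescribes events of any cause.** It is only silent on attribution, and toxicity of the combination could be read as toxicity due to treatment. The firm contrast is with 16.1.1 through 8.2.
- **That the reported rate is biased downward overall.** The six-month window in 16.4 can add events that a 30-day window would miss. The direction is fixed only within a common window.
- **That the mismatch runs both ways.** Related events are a subset of all events, so within one window attribution alone cannot put the related count over a limit that the all-cause count does not reach.

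Three further objections have force. If related covers nivolumab, cisplatin and radiation, few acute events may be excluded. The documents give no figure, but in cohorts of 8 and 4 one patient is enough. Section 16.5 uses the same restriction for chronic toxicity, so it looks deliberate; that explains the choice but does not settle which attribution levels count. Finally, a table by maximum grade and term shows neither 14-day persistence nor completion within 8 weeks, so an all-cause column alone would not reproduce the decision. That objection is right, and the two criteria need their own display.

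**Conclusion.** The point holds as a mismatch between the reported primary result and the events that decide feasibility. In a common window the related-only rate is at most the all-cause rate. One attribution call separates 3/8 from 2/8 in cohort 1, or 2/4 from 1/4 in cohort 2. The likely size is unknown, because it depends on the assumed event rate and related share.

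No go/no-go decision under 16.1.1 changes, and no sample size is affected. The change is still worth making: it concerns the primary endpoint, takes an unblinded judgement out of the headline figure, and costs almost nothing.

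**What to change.** In 16.4:

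1. Make the primary acute-toxicity table all adverse events regardless of attribution, by maximum grade and term, with 90% exact intervals.
2. Show the treatment-related subset alongside, and state which of the five levels in 8.3.1 count as related.
3. Use one acute window, reconciled with 16.1 and 16.2. Section 16.5 starts chronic toxicity beyond six months after radiation, so a 30-day acute window would leave an interval that must be assigned to one table or the other.
4. Replace the feasibility sentence with a reference to 16.1.1, and report each of its two criteria by cohort as a count with an exact 90% interval.

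The cost is one extra column and a short table. With a 30-day window the data are already collected, since 8.5 has all adverse events reported until 30 days after last treatment. With a six-month window, collection must be checked: 8.7 asks for serious events later than 30 days (plus one week) only where a relationship is suspected, so a full all-cause count might not be available.

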16.5 Analysis of Secondary Endpoints

Recurrence patterns within three years of study entry will be described for each cohort, to determine whether there is a difference in patterns (locoregional versus distant).

Chronic treatment-related toxicities will be summarized by maximum grade, experienced beyond six months of completion of radiation therapy.

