1.3 Secondary Objectives

- 1.3.1 To determine site of recurrence, loco-regional versus distant within three years of study entry
- 1.3.2 To estimate the frequency of chronic toxicities experienced within three years after study entry.

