- Cohort TWO: Chemoradiation followed by Nivolumab maintenance for 2 years (total, four patients)
 - o Patients will proceed with definitive chemoradiation alone.
 - o 2-3 weeks following completion, patients will begin Nivolumab 480 mg IV every 4 weeks (+/- 3 days) for a planned duration of 2 years.
- Cohort THREE: Nivolumab 240mg IV during chemoradiation and then as nivolumab monotherapy 480mg IV (beginning no more than 4 weeks post CRT) for 2 years (total, approximately 12 patients to enroll allow for total study)

BrUOG 355: 7/8/17, 7/11/17, 7/20/17, 8/7/17, 8/8/17, 8/14/17, 8/16/17, 8/21/17, 8/22/17, 8/24/17, 8/28/17, 9/5/17, 9/6/17, 9/8/17, 9/11/17, 11/7/17, 11/8/17, 11/19/17 approved DD, 11/20/17, 12/12/17, 12/14/17, 1/29/18, 2/1/18, 2/6/18, 2/7/18, 2/8/18, 2/9/18, 2/12/18, 2/13/18, 3/8/18 all reviews, 3/9/18, 3/13/18, 3/14/18, 3/15/18, 4/19/18, 4/23/18, 5/29/18, 6/5/18, Amendment # 1 7/9/18, Amendment # 2 12/12/18, Amendment #3, 4/6/2020, Amendment #4 5/11/2020

enrollment of up to total 24 patients on study)

- Patients will receive nivolumab during definitive chemoradiation (as in cohort one) followed by nivolumab alone (as in cohort two). Pending safety data of cohort one, patients may be stratified by the radiation field, as in cohort One.

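### In cohorts 2 and 3 the acute and chronic toxicity windows overlap for 19 months or more, so the same on-drug event enters both the primary and the secondary toxicity summaries

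*Combined protocol and SAP*

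**What the plan says.** Section 16.1 makes acute toxicity the primary endpoint. Its general rule is that "acute toxicities will be those having onset during or within 30 days of completing treatment". For maintenance patients it adds: "For those receiving nivolumab as maintenance treatment, it will also include those events occurring during or within 30 days of" treatment completion.

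Section 16.4 gives a different acute window for the analysis: "Acute Treatment-related toxicities that occur during and within six months of study treatment will be summarized by maximum grade". It then states: "Acute toxicities will be used to determine the feasibility within each cohort".

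Section 16.5 defines the secondary endpoint from another anchor, the end of radiation, for all cohorts alike: "Chronic treatment-related toxicities will be summarized by maximum grade, experienced beyond six months of completion of radiation therapy". Objective 1.3.2 sets the far end: "To estimate the frequency of chronic toxicities experienced within three years after study entry".

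Section 5.4 gives the exposure. Cohort 1 has nivolumab before and during chemoradiation only. In cohort 2, "2-3 weeks following completion, patients will begin Nivolumab 480 mg IV every 4 weeks (+/- 3 days) for a planned duration of 2 years". Cohort 3 has nivolumab during chemoradiation, then two years of maintenance starting no later than four weeks afterwards. No section makes acute and chronic mutually exclusive, restricts chronic to radiation effects, or sets a different chronic start for the maintenance cohorts.

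**The concern.** The acute clock stops after the end of all study treatment, whereas the chronic clock starts from the end of radiation. In cohort 1 these two ends nearly coincide. In cohorts 2 and 3 they are about two years apart.

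Take a new treatment-related skin or thyroid event at month 15. In a cohort 3 patient still on maintenance it is acute (primary) and chronic (secondary). In a cohort 1 patient it can only be chronic.

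Two things are at stake. The chronic summary in cohorts 2 and 3 covers mostly time on drug, while in cohort 1 it covers late effects after treatment. The acute summary covers periods of very different length, reported as a maximum grade with no adjustment for time at risk. Cohort 3 combines the treatments of cohorts 1 and 2, so readers will want to set the three sets of rates beside each other.

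**Working it through.** The documents give no overlap figure to reproduce, so this is calendar arithmetic on the stated windows (1 month = 30.4375 days).

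**Inputs**
- Radiation start: two induction doses two weeks apart, then treatment 14 days (+/- 7) after the last dose (5.3, 5.4), so day 21 to 35, nominally day 28.
- Radiation length: the documents give 6 weeks (5.7.5), 60 days (5.7) and up to 66 days as an acceptable variation (5.7.3). I use 42 to 66 days as a range, nominally 42.
- Maintenance start after chemoradiation: 2 to 3 weeks in cohort 2, 0 to 4 weeks in cohort 3. Length: 24 months.
- Patients with maintenance: 4 + up to 12 = 16 of 24 (16.2).
- Assumptions: chemoradiation and radiation end on the same day; study entry is the day of first nivolumab; maintenance runs its planned two years.

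**Step 1. Maintenance left when the chronic window opens.** Maintenance ends (start lag + 24) months after radiation; subtract 6.
- Cohort 2: 24.46 to 24.69, leaving 18.5 to 18.7 months.
- Cohort 3: 24.00 to 24.92, leaving 18.0 to 18.9 months.
- In doses, 19 to 20 of 26 four-weekly infusions fall after the chronic start.

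**Step 2. Time counted as both acute and chronic.**
- Under 16.1, add 30 days (0.99 months): 19.0 to 19.9 months.
- Under 16.4, add 6 months: 24.0 to 24.9 months.

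These figures do not depend on the length of radiation, because both clocks run from its end.

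**Step 3. Share of the chronic window.** Radiation ends (21 + 42)/30.4375 = 2.07 to (35 + 66)/30.4375 = 3.32 months after entry. The chronic window is 36 − (radiation end + 6), or 26.7 to 27.9 months. Double-counted time is about 68% to 75% of it under 16.1 and 86% to 93% under 16.4.

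**Step 4. Length of the acute window by cohort.** Nominally, radiation ends on day 70 (2.30 months), maintenance starts on day 87 (2.86) and ends at 26.86.

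| Rule | Cohort 1 | Cohorts 2 and 3 | Ratio |
|---|---|---|---|
| 16.1 (+30 days) | 2.30 + 0.99 = 3.3 | 26.86 + 0.99 = 27.8 | about 8 |
| 16.4 (+6 months) | 2.30 + 6 = 8.3 | 26.86 + 6 = 32.9 | about 4 |

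**Step 5. Illustration only.** Assume one constant event rate in every month and cohort. Incidence is 1 − exp(−rate × window/12).

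| Assumed rate per patient-year | 16.1: cohort 1 | 16.1: cohorts 2 and 3 | 16.4: cohort 1 | 16.4: cohorts 2 and 3 |
|---|---|---|---|---|
| 0.1 | 3% | 21% | 7% | 24% |
| 0.2 | 5% | 37% | 13% | 42% |
| 0.4 | 10% | 60% | 24% | 67% |

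The rates are not in the documents. The table shows only that identical risk yields different acute percentages.

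**Step 6. Cohort 1.** Its two windows essentially do not overlap. Under 16.1 there is instead a gap of 6 − 0.99 = 5.0 months, from day 31 to month six after radiation, in which an event is neither acute nor chronic. Under 16.4 the windows roughly meet.

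**The case against.** The strongest reply is that 16.1 includes maintenance on purpose. Objective 1.2.2 concerns feasibility of the regimen, which in cohorts 2 and 3 includes maintenance; in cohort 2, where chemoradiation is given without nivolumab, maintenance is the main exposure after induction. This stands: counting maintenance events in the primary endpoint is not itself an error. The fault is that the same events are also called chronic.

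Second, a reader might infer that the overlap distorts the decisions to open cohorts. The documents do not support that. Section 16.1.1 has its own criteria (grade 3 or higher events persisting 14 days or longer; failure to complete chemoradiation in 8 weeks) and its own timing: end of chemoradiation for cohort 1, four weeks into maintenance for cohort 2, and both the end of chemoradiation and the end of maintenance for cohort 3. What is affected is the reported endpoints and the feasibility sentence in 16.4.

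Third, a reader might infer that late on-drug events will dominate the primary rate in cohorts 2 and 3. They occupy most of the window, but event counts are unknown. Toxicity is expected during chemoradiation (7.1.2), and with maximum-grade reporting a later event of the same term at an equal or lower grade adds nothing. Nor is the eightfold ratio a settled figure, since it holds under 16.1 only and is about fourfold under 16.4.

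Fourth, toxicity is descriptive and 16.4 judges feasibility within each cohort, so no planned test is corrupted. That is true and limits the severity, but the published rates would still use one label for different things.

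Finally, 5.5.1 and 7.2 stop treatment for progression and many toxicities, so the overlaps calculated are upper values for patients who stop early.

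**Conclusion.** The point holds as a defect in endpoint definition. In up to 16 of 24 patients, on-drug events over about 19 to 20 months (16.1) or 24 to 25 months (16.4) belong to both toxicity endpoints, and no rule separates them. The acute rates cover periods that differ about eightfold or fourfold between cohort 1 and the others, depending on which acute window applies, so they cannot be read side by side.

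The overlap lengths rest on completion of the planned two years; the window ratios rest also on the nominal schedule; the incidence figures rest on an assumed constant rate and carry no weight beyond illustration. The conflict between 30 days and six months is a separate inconsistency. Resolving it changes the size of the overlap but does not remove it, because the overlap arises while treatment is still being given. The change should be made before analysis, but it does not call the cohort-opening rules into question.

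**What to change.** First reconcile the acute windows in 16.1 and 16.4. The phases below use 30 days, which matches where 8.5 and 8.7 end routine adverse event reporting; if six months is kept instead, the boundaries must move with it. Then assign each event once, by onset date, and report by phase:

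1. **Induction and chemoradiation:** first nivolumab to 30 days after chemoradiation, the same in all three cohorts. Since maintenance starts within four weeks, flag events with onset after the first maintenance dose.
2. **Maintenance (cohorts 2 and 3):** from the end of phase 1 to 30 days after the last maintenance dose. Show it as a separate row of the primary toxicity table, so that the all-treatment total intended by 16.1 is still reported.
3. **Chronic:** onset beyond six months after radiation and outside the on-treatment window. List events persisting from an earlier phase separately and do not count them again.

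Give events in cohort 1 from day 31 to month six after radiation a named category, and use it also for maintenance patients who stop early enough to have such an interval.

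State the limit on ascertainment. Sections 8.5 and 8.7 end routine reporting 30 days after the last treatment (related serious events excepted), while 8.2 says adverse events are recorded for the duration of the trial. These need reconciling, because off-treatment chronic events are the ones that routine reporting would miss.

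The cost is revised wording in 16.1, 16.4 and 16.5 and one more table split, using onset and dosing dates. The downside is smaller chronic counts in cohorts 2 and 3.
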